Grade 4 ^g (QTcF ≥ 501 or > 60 ms change from baseline and Torsades de pointes or polymorphic ventricular tachycardia, or signs/symptoms of serious arrhythmia)	Discontinue patient from study drug treatment, then : 
 - Obtain local cardiologist consultation. - Perform a repeat ECG within one hour of the first QTcF of ≥ 501 ms. - If QTcF remains ≥ 501 ms, repeat ECG as clinically indicated, but at least once a day until the QTcF returns to < 501 ms.
For all grades: 
 • Check the quality of the ECG and the QT value and repeat if needed. • Perform analysis of serum electrolytes (K+, Ca++, Phos, Mg++). If outside of the normal range, interrupt LGX818 and MEK162 and LEE011 administration, correct with supplements or appropriate therapy as soon as possible, and repeat electrolytes until documented as normal. • Review concomitant medication usage for the potential to inhibit CYP3A4 and/or to prolong the QT interval. • Check compliance with correct dose and administration of LGX818 and MEK162 and LEE011. 	
Vascular disorders	
Hypertension	
Grade 1	Maintain dose level of LGX818 and MEK162 (and LEE011 in patients treated in triple-combination arm)
Grade 2	Interrupt dosing until recovery to G1 with proper therapy and monitoring – Re-initiate study drugs at same dose level. If recurs at G2, interrupt study drugs until recovery to G1 and then re-initiate at next lower dose level.
Grade 3 (requiring more than one drug or more intensive therapy than previously)	Interrupt dosing of LGX818 and MEK162 (and LEE011 in triple-combination arm), until resolved to Grade ≤ 1 , then \downarrow 1 dose level* of LGX818 and MEK162 (and LEE011 in triple-combination arm)
Grade 4 (life-threatening)	Discontinue patient from study drug treatment.

Recommended Dose Modifications for (dual) LGX818 and MEK162 or (triple) LGX818 and MEK162 and LEE011 combination study treatment	
Worst Toxicity CTCAE v4.03 Grade (unless otherwise specified)^a	Recommended Dose Modifications any time during a cycle of therapy
Eye disorders	
Retinal events	
Grade 1	Maintain dose level of LGX818 and MEK162 (and LEE011 in patients treated in triple-combination arm) and increase frequency of ophthalmic monitoring to at least every 14 days (see also Section 6.2.6.2).
Grade 2	Maintain dose level of LGX818 and MEK162 (and LEE011 in patients treated in triple-combination arm) and increase frequency of ophthalmic monitoring to at least weekly (see also Section 6.2.6.2). Refer the patient to a retinal specialist within one week for further evaluation. - If resolved to Grade ≤ 1 in ≤ 21 days, then maintain dose level of MEK162 and LGX818 (and LEE011 in patients treated in triple-combination arm) - If not resolved to Grade ≤ 1 in ≤ 21 days, then ↓ 1 dose level* of MEK162 and LGX818 (and maintain dose of LEE011 in patients treated in triple-combination arm). - At any time if symptoms worsen, or persist with the same severity for more than 7 days, reduce 1 dose level ^f of LGX818 and MEK162 (and LEE011 in patients treated in triple-combination arm).
Grade 3	Interrupt dosing of LGX818 and MEK162, (and LEE011 if applicable) until recovery to Grade 1. Re-initiate study drugs at next lower dose level. If recurs at Grade 3, discontinue patient from study. - If resolved to Grade ≤ 1 in ≤ 21 days, then ↓ 1 dose level* of MEK162 and LGX818 (and maintain dose level of LEE011 in patients treated in triple-combination arm) - If not resolved to Grade ≤ 1 in ≤ 21 days, then discontinue patient from study drug treatment and refer the patient to an ophthalmologist for monitoring.
Grade 4 (retinopathy)	Discontinue patient from study drug treatment and refer the patient to an ophthalmologist for monitoring. ⁹
Note: Results and images of ophthalmic examinations must be made available upon request. This includes scans/images of OCTs	
Retinal vein occlusion (RVO)^h	
Any grade	Discontinue patient from study drug treatment and refer the patient to an ophthalmologist for monitoring.
Note: Results and images of ophthalmic examinations should be made available upon request.	

Recommended Dose Modifications for (dual) LGX818 and MEK162 or (triple) LGX818 and MEK162 and LEE011 combination study treatment	
Worst Toxicity CTCAE v4.03 Grade (unless otherwise specified)^a	Recommended Dose Modifications any time during a cycle of therapy
Other eye events (i.e. retinal detachment)	
Grades 1 or 2	Maintain dose level of LGX818 and MEK162 (and LEE011 in patients treated in triple-combination arm) and increase frequency of ophthalmic monitoring to at least every 14 days. At any time if symptoms worsen, or persist with the same severity for more than 7 days, reduce 1 dose level of LGX818 and MEK162. ^c
Grade 3	Interrupt dosing of LGX818 and MEK162 (and maintain dose level of LEE011 in patients treated in triple-combination arm) and refer patient to ophthalmologist monitoring within one week. ^g - If resolved to Grade ≤ 1 in ≤ 21 days, reduce 1 dose level ^h of LGX818 and MEK162 - If not resolved to Grade ≤ 1 in > 21 days, discontinue patient from study drug treatment and refer the patient to an ophthalmologist for monitoring. ^h
Grade 4	Discontinue patient from study drug treatment and refer the patient to an ophthalmologist for monitoring. ^g
Skin and subcutaneous tissue disorders	
Rash / hand foot skin reaction (HFSR) / photosensitivity / Toxic Epidermal Necrolysis (TEN)	
Grade 1	Maintain dose level of LGX818 and MEK162 (and LEE011 in patients treated in triple-combination arm), but consider initiating appropriate skin toxicity therapy (See Appendix 3).
Grade 2	Maintain dose level of LGX818 and MEK162 (and LEE011 in patients treated in triple-combination arm), but initiate/intensify appropriate skin toxicity therapy.
Grade 3 despite skin toxicity therapy	Interrupt dosing of LGX818 and MEK162 (and LEE011 in patients treated in triple-combination arm), until resolved to Grade ≤ 1 then: - If resolved in ≤ 7 days, ↓ 1 dose level* of LGX818 and MEK162 (and LEE011 in triple-combination arm) - If not resolved after > 7 days, discontinue patient from study drug treatment.
Grade 4 despite skin toxicity therapy	Discontinue patient from study drug treatment.

Recommended Dose Modifications for (dual) LGX818 and MEK162 or (triple) LGX818 and MEK162 and LEE011 combination study treatment	
Worst Toxicity CTCAE v4.03 Grade (unless otherwise specified)^a	Recommended Dose Modifications any time during a cycle of therapy
Respiratory, thoracic and mediastinal disorders	
ILD/Pneumonitis	Maintain dose level of LGX818; adjust dose of MEK162 (and LEE011 in patients treated in triple-combination arm) according to Grade below
Grade 1	No dose interruption or adjustment of MEK162 (or LEE011 in patients treated in triple-combination arm) is required. Initiate appropriate medical therapy and monitor as clinically indicated
Grade 2	Interrupt dosing of MEK162 (and LEE011 in patients treated in triple-combination arm) for ≤ 21 days. -If resolved to Grade ≤ 1 in ≤ 21 days, reduce 1 dose level ^h of MEK162 (and LEE011 in patients treated in triple-combination arm), performing an individualized benefit-risk assessment -If not resolved to Grade ≤ 1 in ≤ 21 days, then discontinue patient from study drug treatment. If Grade 2 recurs, discontinue patient from study drug treatment
Grade 3/4	Discontinue patient from study drug treatment
General disorders and administration site conditions	
Fatigue	
Grades 1 or 2	Maintain dose level of LGX818 and MEK162 (and LEE011 in patients treated in triple-combination arm)
Grade 3	Interrupt dosing of LGX818 and MEK162 (and LEE011 in patients treated in triple-combination arm) until resolved to Grade ≤ 1, then: - If resolved in ≤ 7 days, maintain dose level of LGX818 and MEK162 (and LEE011 in triple-combination arm) - If not resolved after > 7 days, then ↓ 1 dose level* of LGX818 and MEK162 (and LEE011 in patients treated in triple-combination arm)
Edema	
Grades 1 or 2	Maintain dose level of LGX818 and MEK162 (and LEE011 in patients treated in triple-combination arm)

Recommended Dose Modifications for (dual) LGX818 and MEK162 or (triple) LGX818 and MEK162 and LEE011 combination study treatment	
Worst Toxicity CTCAE v4.03 Grade (unless otherwise specified)^a	Recommended Dose Modifications any time during a cycle of therapy
Grade 3	Interrupt dosing of LGX818 and MEK162 (and LEE011 in patients treated in triple-combination arm) until resolved to Grade ≤ 1, then: - If resolved in ≤ 14 days, then ↓ 1 dose level* of MEK162 and maintain dose of LGX818 (and LEE011 in patients treated in triple-combination arm) - If not resolved after > 14 days, then discontinue patient from study drug treatment.
Other adverse events	
Grades 1 or 2	Maintain dose level of LGX818 and MEK162 (and LEE011 in patients treated in triple-combination arm)
Grade 3	Interrupt dosing of LGX818 and MEK162 (and LEE011 in patients treated in triple-combination arm) until resolved to Grade ≤ 1, then ↓ 1 dose level* of LGX818 and MEK162 (and LEE011 in triple-combination arm)
Grade 4	Discontinue patient from study drug treatment.

^a All dose modifications should be based on the worst preceding toxicity.

^b Not CTCAE grading

^c Dose reduction below 50 mg QD for LGX818, and below 15 mg BID for MEK162 is not allowed.

^d All patients with ALT or AST >5.0x ULN and total bilirubin > 1.5x ULN in the absence of cholestasis must immediately be withdrawn from study treatment and every attempt should be made to carry out the **liver event follow-up assessments** as described below in [Section 6.3.3](#).
If combined elevations of AST or ALT and total bilirubin do not meet the defined thresholds, please follow the instructions for isolated elevation of total bilirubin and isolated elevation of AST/ALT, and take a conservative action based on the degree of the elevations (e.g. discontinue treatment at the situation when omit dose is needed for one parameter and discontinue treatment is required for another parameter). After all elevations resolve to the defined thresholds that allow treatment re-initiation, re-start the treatment either at the same dose or at one dose lower if meeting a criterion for dose reduction

^e “Cholestasis” defined as: ALP elevation (>2.0 x ULN and R value (ALT/ALP in x ULN) ,2.0) in patients without bone metastasis, or elevation of ALP liver function in patients with bone metastasis.

^f All values refer to the average of triplicate measurements.

^g Ophthalmic monitoring mandated for retinal event, posterior uveitis, RVO: further evaluation with specialized retinal imaging (e.g. ocular coherence tomography, angiography).

^h Except: 1) lymphopenia unless clinically significant, 2) occurrence of KA and/or cutaneous SCC, 3) alkaline phosphatase, 4) AEs not considered clinically significant like alopecia study drug-related fever, electrolyte abnormalities (including K, NA, Cl, HCO₃, Mg, Ca, PO₄).

* ↓ 1 dose level refers to: next lower previously tested dose level of LGX818 and LEE011 and the next lower dose level of MEK162 (please see [Table 6-1](#) and [Table 6-2](#)).

Recommended Dose Modifications for (dual) LGX818 and MEK162 or (triple) LGX818 and MEK162 and LEE011 combination study treatment

**Worst Toxicity CTCAE v4.03 Grade
(unless otherwise specified)^a**

Recommended Dose Modifications any time during a cycle of therapy

** Confounding factors and/or alternative causes for increased transaminases should be excluded before dose interruption/reduction. They include but are not limited to: concomitant medications, herbal preparations or dietary supplements, infection, hepato-biliary disorder or obstruction, new or progressive liver metastasis, and alcohol intake.

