6.3.2 Treatment interruption and treatment discontinuation

Each patient is only allowed a maximum of two dose reductions after which the patient will be discontinued from the study treatment. In addition, a patient should discontinue treatment with the LGX818 and MEK162 dual or LGX818 and MEK162 and LEE011 triple combination if, after treatment is resumed at a lower dose, the toxicity recurs with the same or worse severity. However, the patient may continue to receive study treatment at the next lower dose level, if appropriate, at the discretion of the Investigator and in discussion with the Sponsor. If, after interruption of treatment and resolution, treatment is resumed at the same dose following the criteria in [Table 6-4](#) and the same toxicity recurs with the same or worse severity, next treatment re-initiation must resume at the next lower dose level irrespective of duration. For each patient,

once a dose level reduction has occurred, the dose level may not be re-escalated during subsequent treatment cycles, except in cases where LGX818 dosing was reduced to 450mg QD during MEK162 dosing interruption.

Dose reduction for LGX818 and/or MEK162 and/or LEE011, as applicable means treatment at the next lower dose level of the respective study drug. For LGX818 and LEE011, this is the next lower previously tested dose level. For MEK162 this is the next lower dose level (please see [Table 6-1](#) and [Table 6-2](#)). If a patient requires a dose interruption of >21 days from the intended day of the next scheduled dose, then the patient must be discontinued from the study treatment unless the patient has experienced objective evidence of clinical benefit. If the patient has experienced objective evidence of clinical benefit, and in the opinion of the investigator it is in the best interest of the patient to remain on study, then following discussion with the sponsor, the patient may continue on study treatment.

Table 6-4 Criteria for interruption and re-initiation of LGX818/MEK162/LEE011 triple-combination treatment

Recommended Dose Modifications for (dual) LGX818 and MEK162 or (triple) LGX818 and MEK162 and LEE011 combination study treatment	
Worst Toxicity CTCAE v4.03 Grade (unless otherwise specified)^a	Recommended Dose Modifications any time during a cycle of therapy
No toxicity	Maintain dose level
Blood and lymphatic system disorders	
Anemia (Hemoglobin)	

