Recommended Dose Modifications any time during a cycle of therapy

Investigations (Hepatic^{})**

Bilirubin: total bilirubin without ALT/AST increase above baseline value (confirmed 48-72hr later)^c

Grade 1 (> ULN – 1.5 x ULN)	Maintain dose level of LGX818 and MEK162 (and LEE011 in patients treated in triple-combination arm) with LFTs monitored bi-weekly.
Grade 2 (> 1.5 – 3.0 x ULN)	Interrupt dosing of LGX818 and MEK162 (and LEE011 in patients treated in triple-combination arm) until resolved to Grade ≤ 1, then: - If resolved in ≤ 21 days, then maintain dose level of LGX818 and MEK162 (and LEE011 in patients treated in triple-combination arm) - If resolved in > 21 days, then ↓ 1 dose level* of LGX818 and MEK162 (and LEE011 in patients treated in triple-combination arm) - If not resolved within 28 days, or if toxicity recurs, discontinue patient from all study drug treatment. Repeat liver enzyme and bilirubin tests twice weekly for 2 weeks after dose resumption.
Grade 3 (> 3.0 x ULN)	Interrupt dosing of LGX818 and MEK162 (and LEE011 in patients treated in triple-combination arm) until resolved to Grade ≤ 1, then ↓ 1 dose level - Repeat liver enzyme and bilirubin tests twice weekly for 2 weeks after dose resumption - If not resolved within 28 days, or if toxicity recurs, discontinue patient from all study drug treatment.
Grade 4 (> 10.0 x ULN)	Discontinue patient from study treatment.

Note: If Grade 3 or 4 hyperbilirubinemia is due to the indirect (non-conjugated) component only, and hemolysis as the etiology has been ruled out as per institutional guidelines (e.g., review of peripheral blood smear and haptoglobin determination), then ↓ 1 dose level* and continue treatment at the discretion of the investigator.

AST or ALT without bilirubin elevation > 2 ULN (confirmed 48-72hr later)^c

Grade 1	Maintain dose level of LGX818 and MEK162 (and LEE011 in patients treated in triple-combination arm) and monitor LFTs biweekly.
---------	--

Recommended Dose Modifications for (dual) LGX818 and MEK162 or (triple) LGX818 and MEK162 and LEE011 combination study treatment

Worst Toxicity CTCAE v4.03 Grade (unless otherwise specified)^a

Recommended Dose Modifications any time during a cycle of therapy

AST or ALT without bilirubin elevation > 2 ULN (confirmed 48-72hr later)^c (continued)

Grade 2

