Interrupt dosing of LGX818 and MEK162 (and LEE011 in patients treated in triple-combination arm) until resolved to Grade ≤ 1 (or Grade ≤ 2 in case of liver metastasis), then:
 - If resolved in ≤ 21 days, maintain dose level of LGX818 and MEK162 (and LEE011 for triple-combination arm).
 - If resolved in > 21 days, then ↓ 1 dose level* of LGX818 and MEK162 (and LEE011 for triple-combination arm).
 - If not resolved within 28 days, discontinue patient from all study drug treatment.
Repeat liver enzyme and bilirubin tests twice weekly for 2 weeks after dose resumption.

Grade 3 (> 3.0 x ULN)

Omit dose of LGX818 and MEK162 (and LEE011 in patients treated in triple-combination arm) until resolved to ≤ baseline grade, then ↓ 1 dose level of dose level of LGX818 and MEK162 (and LEE011 in patients treated in triple-combination arm). If not recovered to ≤ baseline grade within 28 days, discontinue patient from all study drug treatment.
Repeat liver enzyme and bilirubin tests twice weekly for 2 weeks after dose resumption. If toxicity recurs, discontinue patient from all study drug treatment.

Grade 4 (> 10.0 x ULN)

Discontinue patient from study drug treatment.

AST or ALT and Bilirubin^d

For patients with normal ALT and AST and total bilirubin at baseline: AST or ALT > 3.0 x ULN combined with total bilirubin > 2 x ULN without evidence of cholestasis^e

Discontinue patient from study drug treatment.

For patients with elevated AST or ALT or total bilirubin at baseline: baseline: (AST or ALT > 2 x baseline AND > 3.0 x ULN) OR (AST or ALT 8.0 x ULN) — whichever is lower — combined with (total bilirubin > 2 x baseline AND > 2.0 x ULN)

Discontinue patient from study drug treatment.

Recommended Dose Modifications for (dual) LGX818 and MEK162 or (triple) LGX818 and MEK162 and LEE011 combination study treatment

Worst Toxicity CTCAE v4.03 Grade (unless otherwise specified)^a

Recommended Dose Modifications any time during a cycle of therapy

Investigations (Metabolic)

Asymptomatic amylase and/or lipase elevation

Grade 1 (> ULN – 1.5 x ULN)	Maintain dose level of LGX818 and MEK162 (and LEE011 in patients treated in triple-combination arm) and initiate appropriate medical therapy and monitoring.

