7.1.4.1 Criteria for premature patient withdrawal

Patients **may** voluntarily withdraw from the study or be dropped from it at the discretion of the investigator at any time. Patients may be withdrawn from the study if any of the following occur:

- Unacceptable AE(s), or failure to tolerate study treatment
- Delay in dosing > 21 consecutive days
- Pregnancy of the patient
- Patient withdrew consent
- Lost to follow-up
- Disease progression
- Initiation of new cancer therapy

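### Section 6.3.2 ends treatment after an interruption of more than 21 days without objective benefit, but the isolated Grade 2 hepatic rows of Table 6-4 restart it up to 28 days with no such condition

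*Protocol*

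**What the plan says.** **General rule.** Section 6.3.2 states: "If a patient requires a dose interruption of >21 days from the intended day of the next scheduled dose, then the patient must be discontinued". The sentence goes on to exempt a patient from discontinuation "unless the patient has experienced objective evidence of clinical benefit". In that case the patient may continue if the investigator judges it to be in the patient's interest and has discussed it with the sponsor. Section 7.1.3 repeats the 21-day limit and the exception, and requires the decision to be documented in the source and the eCRF. Section 7.1.4.1 lists "Delay in dosing > 21 consecutive days" among the reasons for which a patient may be withdrawn from the study.

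**Isolated hepatic rows of Table 6-4.**
- Bilirubin Grade 2: all study drugs are interrupted. Resolution in 21 days or fewer keeps the dose level. Otherwise: "If resolved in > 21 days, then ↓ 1 dose level* of LGX818 and MEK162". The outer limit is "If not resolved within 28 days, or if toxicity recurs, discontinue patient from all study drug treatment".
- AST/ALT Grade 2: the same structure, with the same one-level reduction after more than 21 days. The outer limit is "If not resolved within 28 days, discontinue patient from all study drug treatment".
- Bilirubin Grade 3: interrupt, restart one level lower on recovery, with the same 28-day and recurrence limits as bilirubin Grade 2.
- AST/ALT Grade 3: omit, restart one level lower on recovery. "If not recovered to ≤ baseline grade within 28 days, discontinue patient from all study drug treatment". Recurrence also ends treatment.

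None of these four rows mentions clinical benefit or sponsor discussion, or refers back to the 21-day rule.

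**The concern.** A site managing a slow hepatic recovery would look up both passages. One says that treatment must end after 21 days unless there is benefit. The other contains a branch written for exactly the case of recovery after more than 21 days, and that branch restarts treatment. If the patient has no documented benefit, the site departs from one passage whichever it follows.

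At stake are consistent handling of a safety-relevant toxicity across sites and a clear basis for calling an action a protocol deviation. Section 10.3.3 summarises compliance by counting patients with deviations, and Section 12 permits no authorised deviations.

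**Working it through.** No arithmetic beyond the width of the overlap applies, so the check is a side-by-side reading.

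**1. The express conflict (Grade 2 rows).** Take an isolated Grade 2 ALT elevation with all drugs held from its first day. It resolves on day 24, and the patient has no documented benefit.
- Section 6.3.2: the interruption exceeds 21 days and the exception is not met, so treatment is discontinued.
- Table 6-4, AST/ALT Grade 2: resolved in more than 21 days and within 28, so treatment restarts one dose level lower.

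The bilirubin Grade 2 row gives the same opposition.

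**2. The conflict by implication (Grade 3 rows).** These rows restart on recovery and stop at 28 days or on recurrence. They do not mention day 21, so they do not contradict Section 6.3.2 in words. A site reading the row alone would nonetheless restart on day 24.

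**3. Width of the overlap.** 28 − 21 = 7 days, that is days 22 to 28. This is approximate, because Section 6.3.2 counts from the intended day of the next scheduled dose, whereas the rows count time to resolution and do not define its start. LGX818 and MEK162 are dosed daily without a planned break (Section 6.1.1.2), and all four rows hold both drugs. The difference in clocks therefore shifts the edges of the window but does not remove it.

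**4. Does any text set a precedence?** None was found. Section 6.3.1 says that the dose may be adjusted as the table outlines, and the table calls its contents recommended, whereas Section 6.3.2 uses mandatory wording. That difference in force is suggestive, but it is not a stated hierarchy.

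**5. Is 28 days the table's usual limit?** No. The rows for LVEF decrease, Grade 3 retinal events and Grade 2 ILD/pneumonitis use 21 days as the point of discontinuation, in line with Section 6.3.2. The isolated hepatic rows differ from both.

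**6. Rows not affected.** Grade 4 bilirubin and Grade 4 AST/ALT discontinue at once, as do combined elevations that meet the table's thresholds.

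**The case against.** The best reply is that the passages can be layered: Section 6.3.2 decides whether a patient interrupted for more than 21 days may continue at all, the table then gives the restart dose, and 28 days is an outer hepatic limit. This is a sensible arrangement, and the mandatory-versus-recommended wording fits it. But the protocol does not state it, and it would leave the Grade 2 branch for resolution after more than 21 days wrong, as written, for any patient without benefit.

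Three narrower points stand. The Grade 3 rows conflict only by implication. Section 7.1.4.1 is permissive and concerns withdrawal from the study, so it adds a difference of wording rather than a second contradiction. The two clocks are not identical, so days 22 to 28 is an approximate window.

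A reader might also infer more than the documents support:
- *That the exception is closed to every Phase II patient in the first 8 weeks, before the first scheduled scan.* The protocol does not define objective evidence of benefit as a scheduled RECIST scan. Appendix 1 allows superficial lesions to be measured clinically, and Phase II has physical examinations in Cycles 1 and 2. The first scan also has a ±7-day window.
- *That the primary ORR or DCR is affected.* Under Section 7.2.1 a patient stopped for toxicity still has an End of Treatment scan if the last scan was more than 21 days earlier. Phase II patients then had scans every 8 weeks until Amendment 10 ended that follow-up. Section 10.4.3 counts a failure only when no best overall response can be assessed. Appendix 1 by default excludes scans more than 28 days after the last dose, so an effect on an individual response is conceivable. The documents give no basis for claiming that one occurred or for sizing it.
- *That the patients still on treatment are especially exposed.* Enrolment is closed (Section 14.10.1), and the Amendment 9 rationale describes the patients then continuing as deriving benefit. The 10 still on treatment at Amendment 10 are the likeliest to meet the exception.

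**Conclusion.** The contradiction is real and lies in the current text. It is express in two rows of Table 6-4 (isolated Grade 2 bilirubin and isolated Grade 2 AST/ALT) and implied in two more (Grade 3 of each). It applies to interruptions of about 22 to 28 days in patients without documented objective benefit.

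The conclusion rests on reading the general rule in Section 6.3.2 as applying to hepatic interruptions, since nothing exempts them, and on the absence of any precedence statement. It does not depend on which limit is clinically right, and that is not judged here. No sample size, decision rule or operating characteristic changes. The point is one of internal consistency in a safety-relevant instruction, and it carries no demonstrated consequence for the efficacy analysis.

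**What to change.** Reconcile Sections 6.3.2 and 7.1.3 with the Grade 2 and Grade 3 rows for isolated bilirubin and isolated AST/ALT. The text should state:
- which interruption limit governs these events;
- whether the benefit and sponsor-discussion condition applies to them;
- from which day the interruption is counted.

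Align the wording of Section 7.1.4.1 at the same time. The sponsor's clinical team chooses the limit.

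The cost is one sentence in Section 6.3.2 with a matching reference in 7.1.3, or edits to four table rows. No new listing is needed, because Section 10.5.2.4 already provides for summarising interruptions and listing their reasons by patient.
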